16. DATA AND SAFETY MONITORING PLAN

This study presents no more than minimal risk, however there is still a risk to privacy and confidentiality. Prior to the start of phase 1, the research team from both [REDACTED] NY and [REDACTED] CA met to create a data safety monitoring plan. PIs, team members, and representatives from each study clinic regularly discuss communication and action plans in the unlikely event that an adverse event occurs. Information on how to contact the study team via phone, mail or email is readily apparent to all participating providers and care team members. Though adverse events are not anticipated, should any occur they will be reported to the site PI (“team leader”) in each state and then to the IRB at the time of the event, and copies of all correspondence regarding the event with the IRB will be shared with the CDC, as needed.

17. DATA ANALYSIS PLAN

The primary outcome (receipt of 1+ COVID vaccine) is binary and our main explanatory variable will be an indicator for study arm. We will employ intent-to-treat analyses using generalized linear mixed models (GLMMs) with practice random effects, an approach recommended for group-randomized RCTs in which the goal is to estimate the causal effects of interventions on individuals, adjusted for clustering within groups. This method performs well in situations where the number of observations per cluster is large and for unequal cluster sizes. Models will assume a binomial distribution and a log link function in order to compare vaccination rates between study arms in terms of risk ratios. We will adjust for all practice-level variables included in the randomization balancing criterion, as well as patient-level race/ethnicity. Hypothesis tests will be two-sided with alpha = 0.05. Analyses will be performed

using SAS v. 9.4 (SAS Institute Inc., Cary, NC).

Power Analysis: We conservatively assume a control group vaccination rate of 50% (maximum variance). Adjusting for clustering of patients in practices, and assuming an intraclass correlation (ICC) of 1% (consistent with previous work), this sample size provides 80% power to detect an overall increase of 8.0 percentage point increase in vaccination rates between the QI intervention and control arms. This assumes a chi-squared test (a simplification of the planned mixed model analysis described above), an alpha of 0.05, and a sample size of 5,000 pregnant women organized into 16 practices per study arm.

Final Time/Cost Analysis:

Our two-fold cost measures are (a) total intervention cost to implement the VAX-MOM COVID program aggregated at the three health-system level under a cost analysis and (b) cost per additional COVID vaccination under a subsequent cost-effectiveness analysis. To derive a policy implication regarding the sustainability of programs, we will estimate costs and ICER estimates from the health system perspective.

Costs: To make these cost measures comparable to similar past interventions of reminders and educational programs, we will estimate cost with one-year time horizon, excluding the cost to purchase, store and administer vaccines. We will estimate the total intervention cost, summing non-personnel costs (e.g., EHR hardware, software, and materials) and personnel costs. The personnel costs will distinguish research costs from intervention costs (e.g., practice-level meeting and collecting EHR data). The dollar values of these personnel costs will be calculated by multiplying “time efforts” (weekly reported by study personnel using a REDCap email survey) with the nationally representative “hourly-wage rates” by occupation codes of study personnel, derived from the Bureau of Labor Statistics. We are using this method in an NIH-funded R01 study (the STOP-HPV study) which involves a practice-level intervention to raise HPV vaccination rates and in the original VAX-MOM study; surveys take <1 minute to complete.

Cost-Effectiveness: We will develop a standard decision model for our cost-effectiveness analyses as conducted in our past studies. The effectiveness measures are the rates of COVID vaccination estimated under Aim 2b. We will estimate incremental cost effectiveness ratios (ICERs) for the intervention defined as: $ICER (Study \text{ vs } control) = (cost_{Study} - cost_{Control}) / (COVID \text{ vaccine rate}_{Study} - COVID \text{ vaccine rate}_{Control})$

In the numerator of the equation, the $cost_{Study}$ is standardized to be equal to average intervention cost per patient in a study arm to account for the potential sample size difference between study and control arms.

As explained above, this intervention cost will exclude the cost to purchase, store and administer vaccines, which is assumed to be identical among all practices. Applying the same assumption, the average cost for the control group ($cost_{Control}$) is zero. Using the developed standard decision model, we will conduct probabilistic analyses to generate point estimates and 95% CIs for ICERs and one-way sensitivity analyses to determine conditions for being lower than the thresholds of cost-effectiveness, e.g., healthcare-system based quality improvement

interventions to improve flu vaccination uptake targeting general populations (median ICER \$51 among 23 interventions) and healthcare workers (median ICER \$125 among 6 interventions) reported by a systematic review.

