1. PURPOSE OF STUDY

COVID-19 infection during pregnancy is associated with increased risk of pre-eclampsia, preterm birth and stillbirth.¹ Pregnant women with COVID-19 have a higher rate of ICU admission and intubation than those who are not pregnant.² COVID-19 vaccine is recommended before pregnancy and during pregnancy to decrease the risk of severe illness and death. Pregnant women should also receive a booster dose of COVID-19 vaccine after the original series. A 2022 study showed the effectiveness of maternal vaccination against hospitalization for COVID-19 among infants was 52% overall, 80% during the delta period, and 38% during the omicron period.³ Importantly, studies show that the vaccine is safe and not associated with any negative maternal or infant outcomes.⁴

Despite the benefits of COVID-19 vaccination, only 71% of pregnant women were vaccinated for COVID-19 as of June 2022 (most prior to pregnancy), with a much lower rate of 58% among non-Hispanic Black women.⁵ Additionally, only 56% of pregnant women overall have received a booster, but only 39% of Black pregnant women have received a COVID-19 booster vaccine. **An effective intervention is needed to improve COVID vaccination rates for pregnant women overall, and particularly for Black women.**

Using participating OB/GYN offices affiliated with 3 health systems in [REDACTED], the **VAX-MOM COVID-19 intervention phase will implement a quality improvement initiative aimed at increasing maternal COVID-19 vaccination rates at participating sites.**

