4. STUDY DESIGN & PROCEDURES

Brief Overview of Phase 2:

Using a clustered RCT (randomizing practices), we will allocate half of the practices within each health system to the VAX-MOM COVID-19 intervention and the other half to standard of care (control). We will measure the impact of the intervention on vaccination rates (primary outcomes) as well as rates of vaccination by subgroup (secondary outcomes) (see Table 4). Finally, if VAX-MOM COVID-19 is successful, we will provide the control practices with core intervention materials (e.g., learning module, rate feedback template) at the conclusion of the study.

Design and Procedural Details of Phase 2: (also see Figure 1 for Timeline)

Step 1) Deliver VAX-MOM COVID-19 training to randomized practices:

Randomization Details:

Practices will be the unit of randomization. We will assign practices using a covariate constrained randomization strategy. Practices will be stratified by health system, as well as arm assignment in the primary VAX-MOM trial. Within strata, we will perform constrained randomization to allocate practices to intervention/control arms, and ensure each arm has similar baseline COVID vaccination rates, percent of patients covered by Medicaid, number of OB providers, and number of patients. Specifically, we will use these variables to construct and evaluate a balance criterion, which is the sum of the squared difference between standardized group means on these variables. We will generate all possible combinations of eligible practices in 2 arms (using a SAS macro), and define an acceptable set of randomizations that result in balanced variables (generally the lowest 10% on the balance criterion). From this set of randomizations, we will select one set at random, and then randomly assign each practice to intervention vs control group.

Intervention Details:

Once randomization has been completed, and “intervention group” practices have been identified, multiple quality improvement (QI) techniques will be aimed at practice providers, nurses, and staff.

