2. *Develop PDSA cycle goals on a monthly basis utilizing knowledge about current workflow efficiency and data from vaccine rate reports.* Vaccine champions will utilize the PDSA template (see "*PDSAandTimeCostSurvey...*" document) to guide progress with their respective teams. The template will help them decide upon specific intervention activities appropriate for their setting, track those involved with each activity, compare results from the activity to previous performance, and focus on changes that may need implementation during future cycles. PDSA cycle logs will be sent to vaccine champions for completion via a secure REDCap survey.

For participating [REDACTED] practice sites, the 6-month intervention (entailing PDSA cycles described above) will be extended by 3-5 months (depending upon the original start date of the specific location) until April of 2024, to optimize vaccine intervention efforts and data collection during the peak of the COVID season.

During the 6+-month intervention phase, a study team member may observe intervention sites in-person in order to collect qualitative data regarding workflow and communication techniques as described in the sites' submitted PDSA cycle logs. Specifically, the study team member will document the ways in which the targeted intervention techniques are implemented within the practice (see "*InPersonObservationNotes...*" document). Observation notes will then be compared with submitted PDSA cycle log information and analyzed for consistency.

Of Note: Although study staff will observe OB/GYN practice personnel during patient encounters, practice patients will NOT be the target of the observation, and no identifying patient information will be collected. Rather, the focus of observation will be the select practice personnel only. Any patient-level information recorded during the observation will be done so in a generic manner such that the patient could not be identified on the basis of the notes (e.g., "*...when patient indicated that they did not want the COVID-19 vaccine, the nurse stated, 'The doctor may talk to you more about that when she comes in.'*").

3. *Complete the "Practice Time/Cost Survey" on a monthly basis (see step 4 for further detail).* The vaccine champion will track site personnel attending each rate feedback and PDSA discussion as well as their role (e.g., Ob/Gyn, nurse, desk

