Baseline vaccine rates (reported to each site during their site meeting) were established during the prior protocols (STUDY00007624, STUDY00005115 and STUDY00004408), and contained EHR information from practice patients who were identified as having a live birth within a 6 month time period prior to the start of the intervention.

To establish vaccine rates for the ongoing monthly feedback reports (July 2022 onward), EHR information will be collected every month from intervention sites during the entirety of the intervention phase (see timeline depicted in Figure 1). EHR information will reflect practice patients who are identified as having a live birth on record for that month. Again, all subjects will be female and may be <18 years of age.

To establish the final vaccine data reports (for intervention vs. control comparison), detailed EHR information (see Table 5) will be collected from both intervention and control sites for the entire intervention period, and additionally, any missing data from the baseline period will be collected at this time.

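### The primary model leaves out both stratification factors, so the interval for arm may be wider than the estimate's real spread

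*Combined protocol and SAP*

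**What the plan says.** Section 4 (Randomization Details) names two stratification factors: "Practices will be stratified by health system, as well as arm assignment in the primary VAX-MOM trial". Section 1 gives three systems ("Using participating OB/GYN offices affiliated with 3 health systems in", followed by a redaction). Within strata, the constrained step is meant to "ensure each arm has similar baseline COVID vaccination rates, percent of patients covered by Medicaid, number of OB providers, and number of patients", and the balance criterion is computed from those four variables only.

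Section 17 specifies "generalized linear mixed models (GLMMs) with practice random effects", with a binomial distribution and log link. On covariates it says: "We will adjust for all practice-level variables included in the randomization balancing criterion, as well as patient-level race/ethnicity". On testing it says only: "Hypothesis tests will be two-sided with alpha = 0.05". It names no reference distribution or degrees-of-freedom rule, and no sensitivity analysis adjusted for the strata.

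Two other passages bear on whether the strata could matter. Section 6 says the baseline rates came from "practice patients who were identified as having a live birth within a 6 month time period prior to the start of the intervention". Section 4, Step 2, says that for a redacted group of sites the intervention "will be extended by 3-5 months (depending upon the original start date of the specific location) until April of 2024".

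**The concern.** Splitting practices evenly between arms within each stratum removes stratum-to-stratum variation from the arm comparison. A model without stratum terms does not know this. It leaves that variation in the estimated practice variance, and so in the standard error for arm. The point estimate is unaffected, but its reported precision is understated and the test becomes conservative.

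This needs two conditions. The strata must predict vaccination beyond the baseline rate and the other listed covariates, and arm must be referred to a t distribution on between-practice degrees of freedom. With a normal reference, the small number of practices pushes the error rate up, which can offset or outweigh the conservatism. The covariate list and the degrees-of-freedom rule therefore have to be fixed together.

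At stake is precision that the design has already bought: an interval of the right width, and power for effects below 8.0 points.

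**Working it through.** **1. Parameters.** The planned model has 6 practice-level parameters: intercept, arm and four balancing variables. With 32 practices that leaves 32 - 6 = 26 degrees of freedom. Health system (3 levels) adds 2 and prior arm (assumed 2 levels) adds 1, giving 9 parameters and 32 - 9 = 23.

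**2. The plan's own power figure.** Inputs from Section 17: 5,000 women, 16 practices per arm, ICC 0.01, 50% against 58%, two-sided 0.05.
- 32 practices: 5,000/32 = 156.25 women each; design effect 1 + 155.25 × 0.01 = 2.55; effective n per arm 2,500/2.5525 = 979; power 94.5% at 8.0 points and 79.8% at 6.3.
- 16 practices in total: 312.5 women each; design effect 4.115; effective n per arm 2,500/4.115 = 608; power 80.0% at 8.0 points.

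The stated 80% is not reproduced with 16 per arm, but is with 16 in total (or with an ICC of 2%, 80.1%). That is a separate issue. Here it means that both practice counts must be shown.

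**3. Hand calculation, 32 practices, covariates explaining nothing.** Between-practice variance is 0.01 × 0.25 = 0.0025. Sampling variance of a practice proportion is 0.25/156.25 = 0.0016. Let f be the strata's share of the 0.0025. The half-width is t × √(2V/16).
- Strata omitted: V = 0.0041, SE 2.26 points, × 2.056 (26 df) = 4.65 points, whatever f is.
- Included, f = 0: V = 0.0041; 2.26 × 2.069 (23 df) = 4.68.
- Included, f = 25%: V = 0.001875 + 0.0016 = 0.003475; SE 2.08; half-width 4.31.
- Included, f = 50%: V = 0.00125 + 0.0016 = 0.00285; SE 1.89; half-width 3.91.

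**4. Simulation, 32 practices, t reference.** Practice variance was fixed at 0.0025 and split between strata and residual. There were 3 × 2 strata, even allocation within each, and selection from the best 10% of 200 candidate allocations. The analysis was a linear model of practice proportions. Error rates and power used 8,000 runs per setting, widths 5,000. Each cell gives stratum shares of 0/25/50%.

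| Covariates explain | Type I error, strata omitted (%) | Change in 95% CI width if added (%) | Change in power at 8.0 points | Change in power at 6.3 points |
|---|---|---|---|---|
| 0% | 4.9/3.1/1.8 | +0.5/-7.8/-17.1 | -0.5/+2.1/+3.0 | -0.5/+5.1/+9.8 |
| 30% | 5.0/4.0/2.8 | +0.6/-4.9/-11.5 | -0.2/+0.6/+1.2 | -0.5/+2.5/+5.0 |
| 60% | 5.1/4.6/3.6 | +0.8/-1.7/-5.4 | -0.1/0.0/+0.2 | -0.2/+0.6/+1.3 |

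With the strata included, type I error is 4.6-5.3%. With them omitted and covariates at 0%, power at 8.0 points is 92.0/93.3/95.1%. The paired Monte Carlo standard error of a power change is at most 0.33 points.

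At a 50% share and covariates at 0%, the estimate's actual SD is 1.93 points omitted and 1.92 included, while the mean half-width is 4.70 against 3.90. Only the reported precision differs. A second simulation with stratum sizes 6, 6, 6, 6, 4, 4 (2,500 runs) gave the same half-widths, 4.70 and 3.90, with 2.5% type I error when strata were omitted.

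**5. Normal reference, 32 practices.** Type I error with strata omitted is 6.2/3.8/2.3% (covariates 0%), 5.9/4.9/3.6% (30%) and 6.4/5.6/4.4% (60%). With strata included it is 5.6-6.7%.

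**6. 16 practices in total.** Degrees of freedom are 10 omitted and 7 included. With a t reference, adding the strata changes power at 8.0 points by -4.9/+3.5/+13.5 (0%), -4.6/+0.1/+6.2 (30%) and -3.5/-2.1/+0.1 (60%). With a normal reference and strata included, type I error is 8.4-9.4%.

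**The case against.** The strongest reply is that the baseline COVID vaccination rate is already in the model. Differences between systems or prior arms that existed before the intervention are largely carried by it. If the listed covariates explain 60% of the practice effect, adding strata changes power at 8.0 points by 0.2 or less and narrows the interval by at most 5.4%. The 17.1% figure needs covariates that explain nothing, which is unlikely with the outcome's own baseline among them. This stands, and the 30% and 60% rows are the more realistic ones.

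The counter-argument is that the extended intervention in one group of sites is a difference that a pre-intervention baseline cannot carry. That holds only if the group follows health-system lines, which the redaction hides. Section 4, Step 3, also describes the primary comparison as following a six-month phase. It is a possibility, not evidence.

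Three further points stand. The missing degrees-of-freedom rule is what can push the error rate above 5%, so adding strata without it is no improvement. With 16 practices in total, adding strata loses power in four of the nine settings. The log-link mixed model itself was not simulated, so how reliably it fits with nine practice-level parameters is untested. If the two factors interact, the gain at 8.0 points falls to at most 1.9 points.

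None of this supplies a reason for leaving out the factors the trial randomizes by. At the stated 32 practices, including them costs almost nothing.

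**Conclusion.** The concern holds as a matter of precision. The primary model omits both stratification factors and the plan does not say why. There is no bias. With a t reference on between-practice degrees of freedom, omission makes the test conservative to the extent that the strata are prognostic: type I error of 1.8-4.6% over stratum shares of 25-50%, and an interval that narrows by 1.7-17.1% once the strata are added. If the strata carry nothing beyond the covariates, little changes.

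The plan's ability to detect 8.0 points with 32 practices is not threatened. The gain is a correctly sized interval and more power for smaller effects. The stratum shares, the covariate shares, the two-level prior arm and the 6.3-point effect are assumptions, since the documents give none of them. The change is worth making, with medium confidence in its practical size.

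**What to change.** In Section 17, add health system (3 levels) and arm in the earlier VAX-MOM trial (assumed 2 levels) as main effects in the primary GLMM, alongside the four balancing variables and race/ethnicity. In the same sentence, state that arm is tested on between-practice degrees of freedom, defined as practices minus practice-level parameters: 32 - 9 = 23 if all 32 practices are analysed. The terms should not be added without this rule.

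If the trial in fact has 16 practices in total, settle whether the three extra parameters are included before outcome data are analysed.

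The change is one sentence and one model line, and both variables are already known for every practice. It costs three degrees of freedom. At 32 practices, when the strata explain nothing, that is at most 0.5 points of power and an interval at most 0.8% wider. At 16 in total the corresponding cost is 3.5-4.9 points and an interval about 6% wider (t of 2.365 on 7 df against 2.228 on 10). There is also a loss of 2.1 points there at a 25% stratum share if the covariates explain 60% of the practice effect.

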Effectiveness	
 Primary Outcome: Rate of COVID-19 vaccination (intervention vs control) Secondary Outcomes: 
 COVID-19 vaccination rates by subgroups including (i) insurance groups, (ii) race/ethnicity, (iii) number of pregnancy, (iv) vaccine in prior year Flu and Tdap vaccination rates by subgroups including (i) insurance groups, (ii) race/ethnicity, (iii) number of pregnancy, (iv) vaccine in prior year 	EHR data
Adoption	
 Number and proportion of personnel involved in the VAX-MOM office changes (receiving MOC credit, attending in-office meetings) 	Training attendance records
Implementation	
 Provider and office staff perceptions of feasibility, acceptability, barriers and facilitators to implementation, adherence to intervention, perceived time and cost, and impact on patient flow. Perceived strength of vaccine recommendations. Perceived adherence to staff checking whether vaccine is due. Costs of implementing interventions 	Post-Intervention Survey & Time/Cost Survey
Maintenance	
 Sustainability 	Post-Intervention Survey

Details for EHR data extraction:

- **EHR Measure Description:** We will work with health system EHR report builders and our experienced analysts to build EHR reports which evaluate vaccination coverage at participating sites (see Table 5).

Baseline data was previously gathered during STUDY00007624, STUDY00005115 and STUDY00004408. The remainder of this data (COVID intervention data), as well as any missing baseline data from the protocols listed above, will be gathered under the current protocol STUDY00007717.

Table 5. Data obtained from EHR for women with live births during intervention period

(NOTE: any data missing from the baseline period may also be gathered during Phase 2)

Primary Information	
 COVID-19 vaccination status (both dates and type) Flu vaccination status (dates) Tdap vaccination status (dates)
----------------------------	--

Additional Information: Patient Demographics	
 • DOB • MRN • Date of Delivery • GA at delivery • Race/ethnicity 	
 • Insurance • Language • Parity • High risk status • Other social determinants
Additional Information: Practice Demographics	
 • Site • Provider type (resident, midwife, MD) 	

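### The primary model adjusts for one patient-level variable, race/ethnicity; adding insurance and parity, which are already extracted, would recover a small amount of precision

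*Combined protocol and SAP*

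**What the plan says.** In the combined protocol and SAP, section 17 defines the outcome and the adjustment set: "The primary outcome (receipt of 1+ COVID vaccine) is binary", and "We will adjust for all practice-level variables included in the randomization balancing criterion, as well as patient-level race/ethnicity". The model is a binomial mixed model with a log link and practice random effects.

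The balancing variables are in section 4 (Randomization Details), where the allocation is constrained to "ensure each arm has similar baseline COVID vaccination rates, percent of patients covered by Medicaid, number of OB providers, and number of patients". The primary model therefore already carries practice-level counterparts of prior vaccination and of insurance. At patient level it carries race/ethnicity only: the closing words of the adjustment sentence, "as well as patient-level race/ethnicity", name no other variable.

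Table 5 (section 4) lists the fields to be extracted for each woman, among them "Insurance • Language • Parity • High risk status", together with COVID-19 vaccination dates and type. Table 4 (section 4) lists as secondary outcomes "COVID-19 vaccination rates by subgroups including (i) insurance groups, (ii) race/ethnicity, (iii) number of pregnancy, (iv) vaccine in prior year". Prior-year vaccination is not a Table 5 field and would have to be derived from the dates. Table 4 speaks of number of pregnancy and Table 5 of parity, which are close but not identical.

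**The concern.** The plan treats insurance and prior vaccination as relevant to uptake: it balances the allocation on their practice-level versions and reports rates by their patient-level versions. Only race/ethnicity enters the primary model at patient level, and no reason is given for stopping there.

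Practice-level covariates can absorb differences between practices. They cannot absorb variation between women in the same practice. The constrained allocation balances practices on baseline figures, so the mix of women who deliver later can still differ between arms by chance. What is at stake is the width of the confidence interval for the primary risk ratio.

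**Working it through.** **Inputs.** From section 17: ICC ρ = 0.01, control rate 50%, an 8.0-point increase, 80% power, two-sided alpha 0.05, 5,000 women, 16 practices per study arm. Assumed, because the documents give no value: Rw, the share of within-practice variance that the added covariates explain beyond the present model, at 5-10%; and Rb, the share of between-practice variance they explain, at 0 in the main calculation.

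**1. The plan's own power figure.** Design effect = 1 + (m − 1)ρ; effective n per arm = n / design effect.

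- 5,000 in total, 16 practices per arm: m = 2,500/16 = 156.25; design effect 2.5525; effective n = 979; power 94.5%; detectable difference 6.3 points.
- 5,000 per arm, 16 practices per arm: m = 312.5; design effect 4.115; effective n = 1,215; power 97.7%; detectable difference 5.7 points.
- 5,000 in total, 16 practices in total: m = 2,500/8 = 312.5; design effect 4.115; effective n = 608; power 80.0%; detectable difference 8.0 points.

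Of these, the stated 80% for 8.0 points matches only the third. It is also matched by the first if practice sizes have an unstated coefficient of variation of 1.0. That mismatch is a separate matter. Here it means only that m is uncertain, so both practice sizes are carried forward.

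**2. Patient-level share of the variance.** The variance of an arm mean is proportional to ρ + (1 − ρ)/m, and the patient-level share is s = [(1 − ρ)/m] / [ρ + (1 − ρ)/m].

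- m = 156.25: 0.99/156.25 = 0.00634; s = 0.00634/0.01634 = 38.8%.
- m = 312.5: 0.99/312.5 = 0.00317; s = 0.00317/0.01317 = 24.1%.

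**3. Gain from within-practice variance alone (Rb = 0).** Gain in effective sample size = 1/(1 − s·Rw) − 1.

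- m = 156.25: Rw = 5% gives 1/(1 − 0.0194) − 1 = 2.0%; Rw = 10% gives 1/(1 − 0.0388) − 1 = 4.0%.
- m = 312.5: Rw = 5% gives 1/(1 − 0.0120) − 1 = 1.2%; Rw = 10% gives 1/(1 − 0.0241) − 1 = 2.5%.

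| Reading | Power now | Power, Rw 5% / 10% | Detectable difference now (points) | Detectable difference, Rw 5% / 10% (points) |
|---|---|---|---|---|
| 5,000 total, 16 per arm | 94.5% | 94.9% / 95.2% | 6.31 | 6.25 / 6.19 |
| 5,000 per arm, 16 per arm | 97.7% | 97.9% / 98.0% | 5.67 | 5.64 / 5.60 |
| 5,000 total, 16 in total | 80.0% | 80.4% / 80.9% | 8.00 | 7.96 / 7.91 |

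**4. How demanding the assumed Rw is.** For a binary covariate split 50/50, with overall uptake near 50%, Rw is about the square of the uptake gap. So 5% needs a gap of about 22 points (√0.05 = 0.224) and 10% about 32 points (√0.10 = 0.316). The only vaccination gap by patient group that section 1 gives for the original series is by race: 58% in non-Hispanic Black women against 71% overall. Those 13 points correspond to 0.13² = 1.7%, and race is already in the model. A covariate of that strength would add about 0.7% (m = 156.25: 1/(1 − 0.388 × 0.0169) − 1) or 0.4% (m = 312.5).

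**5. Between-practice variance.** With variance proportional to ρ(1 − Rb) + (1 − ρ)(1 − Rw)/m, setting Rb = 20% and Rw = 0 gives 1/(1 − 0.2 × 0.612) − 1 = 14% (m = 156.25) or 1/(1 − 0.2 × 0.759) − 1 = 18% (m = 312.5). This starts from the full 1% ICC, as if no practice-level covariate were fitted. The model already contains practice baseline vaccination rate and percent Medicaid, so the remaining gain cannot be read off this figure.

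These are approximations on the scale of the plan's own chi-squared calculation, not simulations of the mixed model.

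**The case against.** The strongest case against is that a valid pre-specified model with one demographic covariate is not a defect. The documents report no uptake figures by insurance, parity or prior-year vaccination. The practice-level counterparts of insurance and prior vaccination are already adjusted for. The gain is small, and a short covariate list is a sensible precaution in a log-binomial mixed model with few practices. All of this stands, and it limits the point to a discretionary improvement. It does not remove it: insurance and parity vary between women within a practice, where the present practice-level covariates cannot help, and they draw mainly on thousands of women rather than on the few practice-level degrees of freedom. Using them only in a sensitivity analysis would test robustness but give the primary test no added precision.

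Three stronger readings are tempting and should be resisted.

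- A reader might infer that the plan names these factors as determinants of uptake. Table 4 lists them only as subgroups for secondary outcomes.
- A reader might infer that leaving them out biases the result, since the women are identified after randomisation. Randomisation protects the comparison, chance imbalance is covered by the confidence interval, and the women are not recruited: section 6 takes records of live births at both intervention and control sites.
- A reader might infer a gain of 19-31% in effective sample size, by letting the covariates explain 10-30% of patient-level variance and 20% of between-practice variance. Step 5 shows that 14-18% of that comes from the between-practice assumption alone, part of which the fitted practice-level covariates already take.

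**Conclusion.** The point holds as a minor, optional improvement in precision. Race/ethnicity is the only patient-level covariate in the primary model, while insurance and parity are planned extraction fields. If they explain 5-10% of within-practice variance, the effective sample size rises by about 2-4% with 156 women per practice or 1.2-2.5% with 312, which is worth less than one percentage point of power. That rests on the plan's ICC of 1%, equal practice sizes and an assumed Rw that the documents do not support with data; the true gain could be smaller. Any between-practice gain comes on top but is uncertain.

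Prior vaccination may be the strongest candidate, but it is not safe to add as the plan stands. Section 17 gives the outcome no time window, so a prior-year dose could itself count toward the outcome or fall after the intervention began.

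**What to change.** In section 17:

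- Add patient-level insurance and parity (counted before the index birth) to the covariates of the primary model, with an 'unknown' category for missing values so that no woman is dropped.
- Add prior COVID vaccination only if the outcome is defined to count doses after the practice's intervention start. Define it as doses dated before that start, derived from the extracted dates, and confirm first that the records reach back far enough.
- Pre-specify a fallback in case the log-link model does not converge, such as a logit mixed model with a standardised risk ratio, and state how its confidence interval will be obtained.

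Insurance and parity need no new data. The cost is a few sentences and a possibly harder fit; the fallback keeps the risk-ratio scale but is a different estimator and must be written out. The covariate list should be fixed before outcomes are compared by arm, because choosing it afterwards would be open to challenge.
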